#### **5.4. Secondary Efficacy Endpoints**

See Section 1.1 for a list of the secondary endpoints. All secondary endpoints will be analyzed using observed case data. Additional analyses with specific imputation methods for missing data are added for selected endpoints.

## **5.4.1. Definitions**

### **5.4.1.1. Binary Endpoints**

#### **5.4.1.1.1. NA Treatment Completion Criteria**

NA treatment completion criteria are defined based on the Week 24 results as follows:

- ALT <3x ULN, and
- HBV DNA <60 IU/mL at Week 24 and HBV DNA<LLOQ at the previous visit, or HBV DNA< LLOQ at Week 24, and
- HBeAg-negative, and
- HBsAg <100 IU/mL

*Note:* Participants who are close to meeting the protocol-defined NA treatment completion criteria with the Week 24 results, and do meet the criteria based on the FU Week 2 results may be allowed to stop NA at FU Week 4, after consultation with the Sponsor. In case of ALT elevation  $\geq 3x$  ULN at Week 24, the investigator must consider different potential causes of increased ALT to ensure appropriate work up and management as needed. If the ALT elevation is unrelated to HBV activity and/or <3x ULN by FU Week 2, NA completion may be considered at the discretion of the investigator and in consultation with the sponsor.

The NA completion criteria will be assessed based on clinical laboratory tests and summarized based on the Week 24 (EOSI) or FU Week 2 results, and during the FU phase.

#### **5.4.1.1.2. NA Re-Treatment During Follow-up**

Participants who actually re-started NA treatment during the follow-up phase will be identified based on the ‘Study Drug Administration for NA’ CRF page.

Participants who meet the NA re-treatment criteria will be identified on the CRF page of ‘NA Re-treatment Criteria Assessment’. Each sub-criteria will also be evaluated.

#### **5.4.1.1.3. HBsAg Cut-offs**

The cut-offs for HBsAg level are as follows:

- <1000 IU/mL
- <500 IU/mL
- <100 IU/mL
- <10 IU/mL
- <1 IU/mL
- <LLOQ (0.05 IU/mL)

The cut-offs for HBsAg change from baseline and RTs are as follow:

- decrease by  $\geq 0.3 \log_{10}$  IU/mL
- decrease by  $\geq 0.5 \log_{10}$  IU/mL
- decrease by  $\geq 1 \log_{10}$  IU/mL
- decrease by  $\geq 2 \log_{10}$  IU/mL
- decrease by  $\geq 3 \log_{10}$  IU/mL
- decrease by  $\geq 4 \log_{10}$  IU/mL

#### **5.4.1.1.4. HBsAg Seroclearance**

Seroclearance of HBsAg is defined as a (quantitative) HBsAg level <LLOQ (see [Table 5](#)). HBsAg seroclearance can be observed prior to the time point assessed but must be observed at the given week of interest.

##### **5.4.1.1.4.1. On Treatment**

HBsAg seroclearance will be evaluated over time during the study intervention phase.

##### **5.4.1.1.4.2. Off Treatment**

HBsAg seroclearance will be evaluated over time at each of the FU timepoints separately, with emphasis at FU Weeks 12, 24, 36 and 48 (i.e. 12, 24, 36, 48 weeks after completion of all study interventions at Week 24) and without restarting NA treatment.

For the analyses of seroclearance at the time points mentioned above, participants with HBsAg seroclearance at the respective time points (and without restarting NA treatment during the interval between the time of stopping the study intervention up to the analysis time point (FU Week 12, 24, 36 and 48)) will be considered as having achieved this endpoint.

##### **5.4.1.1.5. Functional Cure**

Functional cure will be evaluated at each of the following time points separately: FU Week 12, 24, 36 and 48. A participant will be defined as having achieved functional cure (FC) if he/she has:

- had HBsAg seroclearance at the given week of interest, and
- not required NA re-treatment between Week 24 and the given follow-up week of interest.

It can be noted that a participant may achieve HBsAg seroclearance prior to the week of interest, but the HBsAg level <LLOQ has to be shown at the given week of interest to be counted as responder.

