6.5.1. NA Treatment Completion

All participants will receive the last dose of JNJ-3989 at Week 24 and the last dose of PegIFN- α 2a at Week 23 (Arms 1 and 2) or Week 11 (Arm 3). They will start the FU Period after the Week 24 visit. If all of the following NA treatment completion criteria are met based on the Week 24 results, treatment with NA will be stopped at the next scheduled visit (ie, FU Week 2):

- The participant has ALT <3x ULN, AND
- The participant has HBV DNA <60 IU/mL at Week 24 and HBV DNA <LLOQ at the previous visit, or HBV DNA <LLOQ at Week 24, AND
- The participant is HBeAg-negative, AND
- The participant has HBsAg <100 IU/mL.

Note: Participants who are close to meeting the protocol-defined NA treatment completion criteria with the Week 24 results, and do meet the criteria based on the FU Week 2 results may be allowed to stop NA at FU Week 4, after consultation with the Sponsor. In case of ALT elevation \geq 3x ULN at Week 24, the investigator must consider different potential causes of increased ALT to ensure appropriate work up and management as needed. If the ALT elevation is unrelated to HBV activity and/or <3x ULN by FU Week 2, NA completion may be considered at the discretion of the investigator and in consultation with the sponsor.

Participants who do not meet the above criteria based on the Week 24 or FU Week 2 results should continue NA treatment during the 48-week FU Period.

Participants who meet the above-mentioned NA treatment completion criteria will be monitored closely during the 48-week FU Period with a study visit at least once every 4 weeks. NA treatment should be re-started in accordance with the NA re-treatment criteria (see Section [6.5.2](#), NA Re-treatment Criteria During Follow-up, for more details).

The investigator should consider to re-start NA treatment per local standard of care at the EOS visit (Follow-up Week 48) for participants who met the NA treatment completion criteria based on the Week 24 (or FU Week 2) results, who did not re-start NA treatment during the follow-up phase, and who did not achieve and maintain HBsAg seroclearance. NA will not be provided by the sponsor after the final study visit.

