ISR	injection site reaction
KPD	kinetic pharmacodynamic model
LLN	lower limit of normal
LLOQ	lower limit of quantification
MDSC	myeloid-derived suppressor cell
MoA	mode of action
MRI	magnetic resonance imaging
MRU	medical resource utilization
NA	nucleos(t)ide analog
NIMP	non-investigational medicinal product
NK	natural killer
NOAEL	no observed adverse effect level
PBMC	peripheral blood mononuclear cell
PD	pharmacodynamic(s)
PegIFN- α 2a	pegylated interferon alpha-2a
pgRNA	pre-genomic ribonucleic acid
PK	pharmacokinetic(s)
PoC	proof of concept
Q4W	every 4 weeks
QW	weekly
QD	once daily
QTcF	QT interval corrected for heart rate according to Fridericia's formula
RBC	red blood cell
rcDNA	relaxed circular deoxyribonucleic acid
RNAi	ribonucleic acid interference
SAE	serious adverse event
SAP	Statistical Analysis Plan
SD	standard deviation
SDM	site-directed mutant
SE	standard error
siRNA	small interfering ribonucleic acid
$t_{1/2\text{term}}$	terminal half-life
T4	thyroxine
TAF	tenofovir alafenamide
TEAE	treatment-emergent adverse event
t_{max}	time to reach C_{max}
TND	target not detected
TNF	tumor necrosis factor
TSH	thyroid stimulating hormone
WBC	white blood cell

Definitions of Terms

ALT/AST nadir	Lowest ALT/AST value during study participation
End of study intervention (EOSI)	Time of the last administration of study intervention
Functional cure (FC)	HBsAg seroclearance at 24-weeks after EOSI
HBsAg or HBeAg seroclearance	HBsAg or HBeAg negativity, respectively, based on the assay used
HBsAg or HBeAg seroconversion	HBsAg or HBeAg negativity and anti-HBs or anti-HBe antibody positivity, respectively
IC ₅₀	half maximal inhibitory concentration
Study intervention	JNJ-73763989 (JNJ-3989), NA (either ETV, tenofovir disoproxil, or TAF), and PegIFN- α 2a
Virologic breakthrough	Confirmed on-treatment HBV DNA increase by $>1 \log_{10}$ IU/mL from nadir or confirmed on-treatment HBV DNA level >200 IU/mL in participants who had HBV DNA level $<$ LLOQ of the HBV DNA assay.

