Week 2), otherwise NA treatment will continue during the complete FU period. Note: Participants who are close to meeting the protocol-defined NA treatment completion criteria with the Week 24 results, and do meet the criteria at FU Week 2 results may be allowed to stop NA at FU Week 4, upon prior discussion with the Sponsor.

The NA treatment completion criteria which take ALT, HBV DNA, HBeAg, and HBsAg levels into consideration, have been selected to ensure that only participants with a higher chance of achieving sustained off-treatment response are allowed to stop all study intervention. Participants who meet the protocol-defined NA treatment completion criteria will be monitored closely during the 48-week FU Period and participants should re-start NA treatment if NA re-treatment criteria are met (see Clinical Protocol Section 6.5.2, NA Re-treatment Criteria During Follow-up, for more details).

If a participant prematurely discontinues JNJ-3989 (ie, before Week 24), the participant will have an early WD visit and will enter the 48-week follow-up period as per the Schedule of Activities, unless the participant withdraws consent.

If a participant prematurely discontinues PegIFN- $\alpha$ 2a (ie, before Week 23 [Arms 1 and 2] or before Week 11 [Arm 3]), treatment with JNJ-3989 and NA should be continued as planned.

If a participant withdraws prematurely from the study, the reason for withdrawal (if known) should be documented in the case report form (CRF) and in the source document. Participants who withdraw consent will be offered an optional safety follow-up visit to occur on the day of consent withdrawal.

An internal Data Review Committee (DRC) will be commissioned for monitoring safety of participants enrolled in this study. In addition, an Independent Flare Expert Panel (IFLEP) will be appointed.

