#### **5.4.1.1.12. Partial Cure**

Partial cure will be evaluated at each of the following time points separately: FU Week 12, 24, 36 and 48. A participant will be defined as having achieved partial cure if he/she has:

- Stopped all study interventions at any time, and
- had HBV DNA level  $< 2,000$  IU/ml at the given follow-up week of interest, and
- had HBsAg  $\geq LLOQ$  at the given week of interest, and
- not required NA re-treatment after stopping all study interventions.

Of note, HBV DNA level  $< 2,000$  IU/ml may be achieved prior to the week of interest but must be observed at the given week of interest.

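### The SAP definition of functional cure does not require NA to have been stopped, so HBsAg below LLOQ on continuous NA counts as functional cure

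*SAP*

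**What the plan says.** SAP 5.4.1.1.5 evaluates functional cure at FU Weeks 12, 24, 36 and 48. A participant achieves it if he or she "had HBsAg seroclearance at the given week of interest, and" has "not required NA re-treatment between Week 24 and the given follow-up week of interest". There is no third condition. The analysis section (SAP 5.4.2.1.5.3) summarizes the proportion by arm and does not restrict it to participants who are off NA.

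The same SAP defines partial cure (5.4.1.1.12) with an explicit first condition, "Stopped all study interventions at any time, and". It ties the re-treatment clause to that stop: "not required NA re-treatment after stopping all study interventions".

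On who stays on NA, the SAP's Figure 1 footnote says that NA stops at FU Week 2 if the completion criteria are met at Week 24, "otherwise NA treatment will continue during the complete FU period". Protocol 6.5.1 says that participants who do not meet the criteria on Week 24 or FU Week 2 results "should continue NA treatment during the 48-week FU Period". The criteria cover ALT, HBV DNA, HBeAg and HBsAg (<100 IU/mL).

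Protocol 2.1 presents functional cure as the off-treatment question of the study. The glossary in Protocol 10.1 defines it as "HBsAg seroclearance at 24-weeks after EOSI".

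**The concern.** A no-re-treatment clause separates off-treatment responders from the rest only if everyone has stopped treatment first. Under the current design some participants never stop NA. They satisfy the clause automatically, so the functional cure count can mix HBsAg loss sustained off all treatment with HBsAg loss under continuing NA. These are different outcomes, and only the first is what the protocol says it wants to explore. There is also an odd ordering: a participant still on NA cannot be a partial cure but can be a functional cure, the stronger claim.

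Functional cure is also used beyond its own table. It enters the virtual-control comparison of HBsAg-based binary endpoints (SAP 5.4.2.1), defines a subset for marker summaries (5.4.2.2.1) and is an outcome in the correlation analyses (Table 6). A misclassified case would carry into all of these.

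**Working it through.** The plan gives no figure for functional cure, so there is none to reproduce. The check traces one participant through the rules and then works out what one such participant is worth.

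**Tracing the rules**

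1. Take a participant whose ALT is at least 3x ULN at Week 24 and FU Week 2, attributed to HBV. The ALT criterion in Protocol 6.5.1 fails, so NA continues through FU Week 48.
2. The re-treatment criteria in Protocol 6.5.2 apply to participants who met the completion criteria. SAP 5.4.1.1.2 identifies re-treatment from CRF pages recording an actual re-start or that the re-treatment criteria were met. Uninterrupted NA is neither, so the second functional cure condition holds.
3. Suppose HBsAg is below 0.05 IU/mL (the LLOQ in SAP Table 5) at FU Week 24. The first condition also holds.
4. The participant is scored as a functional cure at FU Week 24 while taking NA. Under the partial-cure rule the same participant fails at the first condition.

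**Does the re-treatment clause already imply a prior stop?** The partial-cure definition suggests not. It has a no-re-treatment clause of the same kind and still lists stopping as a separate condition. If the clause implied a stop, that condition would be redundant.

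**What one case is worth**

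Inputs: 34 participants per arm (SAP 1.2); two-sided 90% Clopper-Pearson intervals (SAP 5.1.5). The numbers of clearances are assumptions, because the documents give none.

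Effect of one on-NA clearance = 1/34 = 2.9 percentage points. The main functional cure analysis uses observed cases, so the denominator can be below 34 and one case then weighs slightly more; with 30 observed, 1/30 = 3.3 points.

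| Off-NA clearances (assumed) | On-NA clearances (assumed) | Rate as the SAP is written (90% CI) | Rate if NA must be stopped (90% CI) |
|---|---|---|---|
| 0 | 1 | 1/34 = 2.9% (0.2 to 13.2) | 0/34 = 0% (0 to 8.4) |
| 4 | 0 | 4/34 = 11.8% (4.1 to 24.9) | 4/34 = 11.8% (4.1 to 24.9) |
| 4 | 1 | 5/34 = 14.7% (6.0 to 28.5) | 4/34 = 11.8% (4.1 to 24.9) |
| 4 | 3 | 7/34 = 20.6% (10.1 to 35.2) | 4/34 = 11.8% (4.1 to 24.9) |

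The table shows sensitivity to the rule. It is not a forecast.

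**How many cases are plausible?** A participant kept on NA because HBsAg is at least 100 IU/mL would need a further fall of at least log10(100/0.05) = 3.3 log10 after JNJ-3989 has ended, which is a narrow route. A participant with HBsAg already below LLOQ at Week 24 meets the HBsAg criterion and would stay on NA only because of ALT, HBV DNA or HBeAg, or because the stop rule was not followed. Protocol 6.5.1 narrows the ALT route, since NA completion may still be considered if the elevation is unrelated to HBV activity or has fallen below 3x ULN by FU Week 2. The number is therefore unknown and may be small.

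**The case against.** The strongest reply is that the listed off-treatment endpoints are already protected. Functional cure is not in the objectives and endpoints tables of either document. The listed secondary endpoint is HBsAg seroclearance at FU Weeks 24 and 48 without re-starting NA, under an objective limited to participants who met the completion criteria. Its analysis section (SAP 5.4.2.1.5.2) requires all study interventions to be stopped and adds a summary whose denominator includes only participants who are off NA. The HBV DNA analysis (5.4.2.1.10) does the same. This stands. A reader might infer that those endpoints share the gap, but they do not. At most, their definitions in 5.4.1.1.4.2 and 5.4.1.1.10 could be worded to match the analysis sections. These tables would also let a careful reader see a discrepancy with the functional cure rate, although they do not correct it.

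A second reply concerns the glossary. It defines EOSI as "Time of the last administration of study intervention", and study intervention includes NA, so a reader might infer that the protocol times functional cure from the last NA dose. The documents mostly use EOSI to mean Week 24, in the primary endpoint and elsewhere, and participants who meet the criteria still take NA until FU Week 2 or FU Week 4. The glossary therefore does not settle the matter. The conflict rests on Protocol 2.1 and on the partial-cure definition.

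A third reply is that the effect has no documented size. This also stands.

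**Conclusion.** The point holds. As written, SAP 5.4.1.1.5 counts a participant on continuous NA with HBsAg below LLOQ as a functional cure, against the off-treatment meaning in Protocol 2.1 and the stop condition in the SAP's partial-cure definition. This is a stated rule that misclassifies, not a missing detail.

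Its reach is limited. Functional cure is descriptive, so the primary test, sample size and type I error are unaffected. Each affected participant moves an arm's rate by 2.9 points on a denominator of 34. That matters most when true off-NA cures are few: with none, a single case would turn 0% into a reported functional cure.

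Two stronger readings are not supported. One is that the rate will be materially inflated; no document gives an expected number of on-NA clearances. The other is that the error will favour Arms 1 and 2, because PegIFN-α2a runs to Week 23 there and raised ALT could block NA stopping. That is conceivable, but no figure supports it, and Protocol 2.3.3 says that the effect of adding PegIFN-α2a to JNJ-3989 on ALT elevations is not known in HBV mono-infection.

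**What to change.** Add a third condition to SAP 5.4.1.1.5: all study interventions, including NA, were stopped before the week of interest, and NA was not restarted between that stop and the week of interest. Score participants still on NA at that week as not achieving functional cure, keep them in the denominator, and tabulate HBsAg below LLOQ on NA as a separate category by arm. Use the revised definition in the virtual-control, marker and correlation analyses that use functional cure.

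For seroclearance and HBV DNA, no change to the analyses is needed. At most, align the definitions in 5.4.1.1.4.2 and 5.4.1.1.10 with the stop condition in 5.4.2.1.5.2 and 5.4.2.1.10.

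The cost is a few lines of SAP text and a programming check against NA administration data that are already collected. The reported functional cure rate may be slightly lower. Make the change before functional cure is first analysed; in an open-label study with several interim analyses, a later change could look data-driven.

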##### **5.4.1.1.6. Treatment Failure**

A participant will be defined as on-treatment failure if he/she didn't have a reduction from baseline of at least  $2 \log_{10}$  IU/mL levels at Week 24.

#### **5.4.1.1.7. HBsAg Seroconversion**

Seroconversion of HBsAg is defined as having achieved HBsAg seroclearance and appearance of anti-HBs antibodies.

The seroconversion will only be assessed at the time points when the anti-HBs antibodies assessment is available.

Appearance of anti-HBs antibodies is defined as a baseline anti-HBs antibodies (quantitative) <LLOQ and a post-baseline assessment  $\geq$ LLOQ. An additional seroconversion will be applied using the threshold of 10 mIU/mL, i.e. appearance of anti-HBs antibodies is defined as a baseline anti-HBs antibodies (quantitative) <10 mIU/mL and a post-baseline assessment  $\geq$ 10 mIU/mL.

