5.1. Inclusion Criteria

Each potential participant must satisfy all of the following criteria to be enrolled in the study:

A01 (adapted from M01) Adult male or female participants ≥ 18 (or the legal age of consent in the jurisdiction in which the study is taking place) to 65 years of age, inclusive.

M02 Participants must be medically stable based on physical examination, medical history, vital signs, and 12-lead ECG performed at screening. If there are abnormalities, they must be consistent with the underlying illness in the study population. This determination must be recorded in the participant's source documents and initialed by the investigator.

A03 (adapted from M03a) Participants must have chronic HBV infection. HBV infection must be documented by serum HBsAg positivity at screening. In addition, chronicity must be documented by any of the following, at least 6 months prior to screening: serum HBsAg positivity, HBeAg positivity or HBV DNA positivity, ALT elevation above ULN without another cause than HBV infection, documented transmission event. If none of the above are available, the following ways of documenting chronicity are acceptable at the time of screening: liver biopsy with changes consistent with chronic HBV, or absence of marker for acute HBV infection such as positive immunoglobulin M (IgM) anti-hepatitis B surface (HBs) and anti-HBc antibodies.

Participants should:

- be HBeAg-negative, AND
- be anti-HBe antibody-positive, AND
- be on stable HBV treatment, defined as currently receiving NA treatment for at least 2 years prior to screening, and having been on the same NA treatment regimen (at the same dose) as used in this study for at least 3 months at the time of screening, AND
- have documented serum HBV DNA < 60 IU/mL on 2 sequential measurements at least 6 months apart (one of which is at screening), AND
- have documented ALT values $< 2.0 \times$ ULN on 2 sequential measurements at least 6 months apart (one of which is at screening).

M04 Participants must have a body mass index (BMI; weight in kg divided by the square of height in meters) between 18.0 and 35.0 kg/m², extremes included.

A05 (adapted from M05)	Participants must sign a Master ICF (specific for the Master Protocol PLATFORMPAHPB2001) and must sign the ICF specific for this intervention cohort, indicating that he or she understands the purpose of, and procedures required for, the study and is willing to participate in the study.

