#### 5.5.1.3.4. Time to Appearance of Anti-HBe Antibodies

Appearance of anti-HBe antibodies is defined as a baseline anti-HBe antibodies (qualitative) with a "NEGATIVE" result and a post-baseline assessment with "POSITIVE" result.

Time to appearance of anti-HBe antibodies is defined as the time (days) from the date of first study intervention intake to the date of the first occurrence of anti-HBe antibodies appearance + 1. The participants who did not experience emergence of antibodies or who early withdrew from the study before showing emergence of anti-HBe antibodies will be censored at the last anti-HBe antibodies assessment before the date of withdrawal.

Time to appearance of anti-HBe antibodies will be also analyzed considering the participants who were retreated with NA before achieving appearance of anti-HBe antibodies as censored at the date of NA retreatment.

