### **5.5.2.2.3. Anti-HBs Antibodies**

The actual values of and changes from baseline in anti-HBs antibodies will be summarized only descriptively in a similar manner as described for values and changes from baseline over time in other blood disease markers in Section 5.4.2.2.1.

For all participants with positive anti-HBs antibodies at baseline who will reach HBsAg seroclearance (as defined in Section 5.4.1.1.4), descriptive statistics will be calculated for the change of anti-HBs antibodies level from baseline at the timepoint when achieving the HBsAg seroclearance. In an additional summary, the change of anti-HBs antibodies level from baseline at the specific timepoint will be summarized descriptively for the subset of the participants achieving HBsAg seroclearance at any time before or at that given timepoint.

Cross-tabulations overtime of quantitative versus qualitative anti-HBs values, respectively, will also be presented.

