**6.2. Appendix 2 Changes to Protocol-Planned Analyses**

There are no changes to the protocol-planned analyses.

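### The SAP narrows the protocol's HBsAg seroconversion endpoint to new antibody from a negative baseline without declaring it, and its anti-HBe appearance analysis has almost nobody at risk

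*SAP*

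**What the plan says.** **Seroconversion.** Protocol Appendix 1 (10.1) defines seroconversion as "HBsAg or HBeAg negativity and anti-HBs or anti-HBe antibody positivity, respectively". The proportion with HBsAg seroconversion is a secondary endpoint in both documents.

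SAP 5.4.1.1.7 says "Seroconversion of HBsAg is defined as having achieved HBsAg seroclearance and appearance of anti-HBs antibodies", and then "Appearance of anti-HBs antibodies is defined as a baseline anti-HBs antibodies (quantitative) <LLOQ and a post-baseline assessment" at or above that limit. SAP Table 5 puts the anti-HBs LLOQ at 5 mIU/mL. The same section adds "An additional seroconversion will be applied using the threshold of 10 mIU/mL", which needs a baseline below 10 and a later value of at least 10. SAP 5.4.1.3.2 carries the appearance requirement into time to first seroconversion. SAP 5.4.2.1.7 summarizes the proportion by arm and phase without limiting the denominator to participants who start below the cut-off.

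**Who can enrol.** Protocol 5.1 and 5.2 do not exclude anti-HBs-positive participants. Anti-HBs is mentioned only as an IgM marker in a fallback route for documenting chronic infection. The SAP expects such participants: Table 12 tabulates baseline anti-HBs status, Table 8 has a subgroup at or above 10 mIU/mL, and 5.5.2.2.3 plans a summary "For all participants with positive anti-HBs antibodies at baseline who will reach HBsAg seroclearance".

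**Anti-HBe.** Inclusion criterion A03 requires participants to "be anti-HBe antibody-positive, AND" meet its other conditions. SAP 5.5.1.3.4 reads "Appearance of anti-HBe antibodies is defined as a baseline anti-HBe antibodies (qualitative) with a" negative result, followed by a positive one after baseline. Everyone without that change is censored.

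**Declared changes.** SAP Appendix 2 (6.2): "There are no changes to the protocol-planned analyses".

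**The concern.** The two documents use one name for two endpoints. Take a participant with anti-HBs of 12 mIU/mL at baseline who clears HBsAg with anti-HBs at 500 mIU/mL. The protocol counts a seroconversion. Both SAP versions count a non-event, and the time-to-event analysis censors the participant. Events are likely to be few in a trial of 34 per arm, so single participants matter to the reported rate. A reader comparing the report with the protocol would not learn from Appendix 2 that the definition had been tightened.

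The anti-HBe analysis has the opposite fault. Nearly every participant enters it already past the event, so its curves say nothing about treatment, yet a flat line could be read as no effect.

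**Working it through.** The documents state no rate, power or sample size for seroconversion or for anti-HBe appearance, so there is no figure of the plan's own to reproduce. The check compares definitions and adds an illustration on assumed inputs.

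**1. Direction.** At a fixed cut-off and visit, the SAP event is the protocol event plus one further condition (baseline below the cut-off). SAP events are therefore a subset of protocol events. The denominator is the same, so the SAP proportion cannot exceed the protocol proportion.

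**2. Size.** Let N = 102 (SAP section 3), f = share at or above the cut-off at baseline, and s = true rate of protocol-defined seroconversion. Neither f nor s is in the documents. Assume that clearance is independent of baseline anti-HBs.

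- Participants who can never be counted: N × f
- Protocol-defined events expected: N × s
- Events lost: N × f × s, which is a fraction f of all events

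With s = 10%, 102 × 0.10 = 10.2 events are expected under the protocol definition.

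| Assumed f | Never countable (102 × f) | Events lost (10.2 × f) | Events left |
|---|---|---|---|
| 2% | 2.0 | 0.2 | 10.0 |
| 5% | 5.1 | 0.5 | 9.7 |
| 10% | 10.2 | 1.0 | 9.2 |
| 20% | 20.4 | 2.0 | 8.2 |

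Over f = 5-20% and s = 5-20%, the loss runs from 102 × 0.05 × 0.05 = 0.3 to 102 × 0.20 × 0.20 = 4.1 events.

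**3. The two SAP versions are not nested.** Take baseline anti-HBs 7 mIU/mL, then 500 mIU/mL with HBsAg cleared.

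- LLOQ rule: 7 is not below 5, so no event.
- 10 mIU/mL rule: 7 is below 10 and 500 is at least 10, so an event.

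Raising the positivity cut-off has added a responder. That cannot happen when the endpoint rests on positivity at the visit alone. The 10 mIU/mL version thus recovers participants who start between 5 and 10 and later reach 10, but not those who start at 10 or above.

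**4. Anti-HBe risk set.** A03 makes every eligible participant anti-HBe-positive at screening. SAP 5.1.4 takes baseline as the last value before first dose, and the Schedule of Activities samples anti-HBe at both screening and Day 1. If Day 1 agrees with screening, the number at risk is 0 of 102. The Kaplan-Meier incidence is then 0% in every arm, and the log-rank comparison (SAP 5.5.2.3, referring to 5.4.2.3) has no events. Only an entry deviation or a negative Day 1 result can supply one.

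**5. Contrast within the SAP.** It limits the analysis to participants who can have the event for time to HBV RNA below LOD (5.5.1.3.1), for time to HBcrAg undetectability (5.5.1.3.2) and for ALT normalization (5.4.2.1.11). It does not do so for seroconversion or for anti-HBe appearance.

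**The case against.** The best defence is that requiring new antibody is a deliberate and stricter choice. The protocol gives no numeric anti-HBs cut-off and leaves technical detail to the SAP (sections 9 and 9.4), so the SAP had to make the endpoint operational. The protocol definition has its own weakness: someone at 12 mIU/mL at baseline who clears HBsAg and stays at 12 becomes a seroconversion with no change in antibody. This part stands, and it is a reason to report both forms. It does not explain an undeclared departure, or a denominator that keeps people who cannot have the event.

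A reader might infer that these participants drop out of the efficacy results. They do not. They still count towards HBsAg seroclearance and functional cure, neither of which has an antibody condition, and SAP 5.5.2.2.3 describes their antibody change. That summary does not return them to the seroconversion count.

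A reader might also infer a loss of one or two events in ten. An assumed f of 5-10% does not give that under independence. It would take f of 10-20%, or a link between baseline antibody and clearance that the documents do not describe.

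Finally, anti-HBe appearance is exploratory, its comparisons carry no multiplicity control, and it is not named among the objectives. Baseline anti-HBe status and the shift tables will be visible beside it, so an empty curve is more redundant than misleading. That is fair, and it keeps this part minor.

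**Conclusion.** The discrepancy is real. The SAP narrows a protocol-defined secondary endpoint, keeps participants who cannot meet the narrower rule in the denominator or as censored, and declares no change. The error runs one way, towards understating the rate. The expected loss is a fraction f of protocol-defined seroconversions, about 0.5 to 1 of 10 at an assumed f of 5-10%. This rests on two things the documents do not supply: the prevalence of baseline anti-HBs, and independence of clearance from it. If no participant at or above the cut-off at baseline clears HBsAg, nothing is lost.

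Time to anti-HBe appearance is structurally empty. To say that the event cannot occur would go too far, because an entry deviation or a negative Day 1 result could still produce one. Nothing here touches the primary endpoint, its power or its multiplicity control.

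**What to change.** - In SAP 5.4.1.1.7 and 5.4.1.3.2, define seroconversion as in the protocol: HBsAg below LLOQ and anti-HBs at or above the stated cut-off at that visit. Report this as the secondary endpoint.
- Report new appearance of anti-HBs as a separate analysis, with the denominator and risk set limited to participants below the cut-off at baseline. New antibody can then be told apart from unchanged pre-existing antibody.
- List any departure that remains in SAP Appendix 2.
- Delete the Kaplan-Meier and log-rank analysis of anti-HBe appearance, or limit it to participants who are anti-HBe-negative at baseline. The shift tables already planned in SAP 5.5.2.1.4 show changes in either direction. A new endpoint of anti-HBe loss is optional, since no protocol objective asks for it.

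The cost is SAP wording and reprogramming of these derivations, with no new data. The small downside is two versions of seroconversion to report, one of which also counts antibody that was present before treatment.
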